6.3.1.6 Impact of Concomitant AED Medication Use on Seizure Frequency

Subjects in the study were required to be on stable background therapy for the first 6 months of treatment, after which background AEDs could be reduced or withdrawn so long as one background AED remained. The percentage of subjects who had changes in dose or type of concomitant AED medications during the first, second, third, fourth, fifth, and sixth months will be summarized by treatment group and overall.

6.3.2 Other Effectiveness Analyses – Seizure Related

6.3.2.1 Non-convulsive Seizure Frequency per 28 Days

Similar methods as described above will be used to assess the frequency of non-convulsive seizures per 28 days.

6.3.2.2 Convulsive and Non-convulsive Seizure Frequency per 28 Days

The frequency of seizures (convulsive and non-convulsive) will be analyzed using methods similar for the analysis of convulsive seizure frequency per 28 days as described above.

6.3.2.3 Percentage of Subjects with $\geq 50\%$ Reduction from Baseline

A response curve will be generated for the mITT population. This graph will plot the percentage of subjects (y-axis) against percentage reduction in seizure frequency per 28 days in the OLE treatment period (x-axis). In the graph, subjects experiencing an increase in seizure frequency will be regarded as having a 0% reduction in seizure frequency. Hence, the ordinate for time point 0 may not necessarily be at 100%. For example, if 15% of subjects have no reduction in seizure frequency between baseline and OLE Treatment period, the graph will start on the y-axis at 85%. The graph will be generated for all subjects (excluding de novo subjects), and for each age stratum and each treatment group. A separate graph will be generated for de novo subjects.

A point estimate and 95% confidence interval for the percentage of subjects achieving a $\geq 50\%$ reduction from baseline (Core) to OLE Treatment period, and monthly periods of the OLE will be computed. This will be repeated for the Month 2 to EOS endpoint. The confidence interval for the proportion will be based on the normal approximation to the binomial distribution. The analysis will be computed for the mITT population excluding de novo subjects, and, separately, for the de novo subjects.

Similar methods will be used to estimate the proportion of subjects who achieve a 25%, reduction, 75% reduction, and 100% reduction in seizures.

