Pre-OLE	N/A	-1	Core Study Final * Week	End of T+M in Core Study – 6 days, to End of T+M in Core Study
Pre-OLE de novo	N/A	-99	Baseline (OLE)*	Day -28 to Day -1 of Study ZX008-1503
OLE	3	1	Month 1 (OLE)	1-30
OLE	4	2	Month 2 (OLE)	31-60
OLE	5	3	Month 3 (OLE)	61-90
OLE	6	4	Month 4-6 (OLE)	91-180
OLE	7	5	Month 7-9 (OLE)	181-270
OLE	8	6	Month 10-12 (OLE)	271-360
OLE	9	7	Month 13-15 (OLE)	361-450
OLE	10	8	Month 16-18 (OLE)	451-540
OLE	11	9	Month 19-21 (OLE)	541-630
OLE	12	10	Month 22-24 (OLE)	631-730
OLE	13	11	Month 25-27 (OLE)	731-820
OLE	14	12	Month 28-30 (OLE)	821-910
OLE	15	13	Month 31-33 (OLE)	911-1000
OLE	16	14	Month 34-36 (OLE)	1001-1095
OLE	NA	99	Month 01-EOS (ENDPT1)	1 to min(Last Dose date, Visit 16 date)
OLE	NA	98	Month 02-EOS (ENDPT2)	31 to min(Last Dose date, Visit 16 date)

Note: EOS/ET date = Visit 16 date. Per protocol, Visit 17 is end of the OLE Phase.

T+M=Titration + Maintenance in Core Study.

*Subjects in Study ZX008-1504 Cohort 1 will not have a baseline(core), For those subjects, the Core Study(T+M) represents all their seizure data during the transition period in the core study. Their core study final week will be the last 7 days of seizure data prior to the first visit in ZX008-1503. De novo subjects start Study ZX008-1503 treatment after a screening period.

**Analysis visit numbers are not the same as nominal visit numbers.

Table 7b. Time Intervals for Questionnaires*

Analysis Phase/Period	Scheduled Visit Number in ZX008-1503	Analysis Visit Number*	Time Interval (label on output)	Time Interval (Day)	Target Time Point (Day)
Pre-OLE	N/A	-99	Baseline (Core)	<1	Core Study Day -42 to Day-1 of Core Study
Pre-OLE	1	1	Baseline (OLE)	1	1
OLE	3	3	Month 1 (OLE)	21 to 44	30
OLE	4	4	Month 2 (OLE)	45 to 74	60
OLE	5	5	Month 3 (OLE)	75 to 134	90
OLE	6	6	Month 6 (OLE)	135 to 224	180
OLE	7	7	Month 9 (OLE)	225 to 314	270
OLE	8	8	Month 12 (OLE)	315 to 409	365
OLE	9	9	Month 15 (OLE)	410 to 499	455
OLE	10	10	Month 18 (OLE)	500 to 589	545
OLE	11	11	Month 21 (OLE)	590 to 679	635
OLE	12	12	Month 24 (OLE)	680 to 774	730
OLE	13	13	Month 27 (OLE)	775 to 864	820
OLE	14	14	Month 30 (OLE)	865 to 954	910
OLE	15	15	Month 33 (OLE)	955 to 1044	1000
OLE	16	16	Month 36 (OLE)	1045 to 1109	1095
OLE	OLE Last Visit**	99	Last Value	Day 2 to Visit 17 date	

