	95%CI*	XX.X%, XX.X%	XX.X%, XX.X%	XX.X%, XX.X%	XX.X%, XX.X%	XX.X%, XX.X%	XX.X%, XX.X%

mITT = Modified Intent-to treat; CI = Confidence Interval; *Exact Clopper-Pearson CI. # Excludes the De Novo subjects.

TLF Shells

Zogenix International Limited
ZX008-1503

[1]Baseline=Baseline prior to double-blind treatment in the core study. Subjects in 1504-C1 do not have a Baseline(Core), and are not included in this table.

Programming Note: Repeat for months 2, 3, 6, 9, 12, 15, 18, 21, 24, 27, 30, 33, and 36. Use the Table 14.2.2.1 shell for

Table 14.2.2.1.1
Percent Reduction in Convulsive Seizure Frequency, OLE Treatment Period
mITT Population (Japan)

[figure not shown]
Figure 14.2.2.2
Cumulative Response Curves for Percent Reduction in CSF during OLE Treatment Period
mITT Population

Example graph: From PROC LIFETEST.

Zogenix Inc.
Protocol: ZX008-VS01

Page 1 of 1

Figure A14.2.2.2.1
Cumulative Response Curve for % reduction in seizure frequency per 28 days
mITT Population

Program: rgkmttest_strpntl.sas Output: FA14_02_02_02_01.rtf

Date: 06APR2018 15:45

Example graph above: use rgkmttest_strpntl.sas

Programming Note: Use the Figure 14.2.2.2 shell for

Figure 14.2.2.2.1
Cumulative Response Curves for Percent Reduction in CSF during OLE Treatment Period
mITT Population (Japan).

Footnote: mITT = Modified intent-to-treat population.

Table 14.2.3.1
Duration of the Longest interval (days) between convulsive seizures
mITT Population

	PBO-ZX008 OL (N = XX)	ZX 0.2 – ZX008 OL (N = XX)	ZX 0.5 – ZX008 OL (N = XX)	ZX 0.8 – ZX008 OL (N = XX)	ZX008 OL (N = XX)	De Novo Subjects (N = XX)
n	XX	XX	XX	XX	XX	XX
mean	XX.x	XX.x	XX.x	XX.x	XX.x	XX.x
SD	XX.xx	XX.xx	XX.xx	XX.xx	XX.xx	XX.xx
Min	XX	XX	XX	XX	XX	XX
25 th Percentile	XX.X	XX.X	XX.X	XX.X	XX.X	XX.X
Median	XX.X	XX.X	XX.X	XX.X	XX.X	XX.X
75 th Percentile	XX.X	XX.X	XX.X	XX.X	XX.X	XX.X
Max	XX	XX	XX	XX	XX	XX

mITT = Modified Intent-to-treat; CI = Confidence Interval;

Note: Percentages are calculated based on the number of subjects with non-missing data in the modified ITT population.

Figure 14.2.3.2
Boxplot of Distribution of Duration of Longest Interval between Convulsive Seizures during OLE Treatment Period
mITT Population

Programming notes:

Footnote: mITT = Modified intent-to-treat population

[figure not shown]
Example only: Separate boxplot for each group.

For interim analysis, if done, use only one box, for Group 9 (ZX008 OL, All Subjects)

Zogenix Inc.
Protocol: ZX008-VS01

Page 1 of 1

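### The seizure-free (=100% reduction) proportion is tabulated as one monthly series although its window lengthens from 30 to 90-100 days after Month 3, which builds in a downward step at Month 4-6

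*SAP*

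**What the plan says.** Section 6.3.2.3 asks for the proportion with at least a 50% reduction from Baseline (Core) over the whole OLE period, over Month 2 to EOS, and by period within the OLE: "monthly periods of the OLE will be computed". It then extends the method to the other thresholds: "Similar methods will be used to estimate the proportion of subjects who achieve a 25%, reduction, 75% reduction, and 100% reduction in seizures".

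The seizure windows are in SAP Table 7a (section 6.1.6). The early ones are single months, for example "Month 1 (OLE) 1-30" and "Month 3 (OLE) 61-90". The next entry is "Month 4-6 (OLE) 91-180", and the later ones continue in that style, for example "Month 22-24 (OLE) 631-730". Section 6.3.1.1 derives interval seizure frequency for these 14 intervals, as 28 times the count divided by the days with diary data.

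The shell for Table 14.2.2.1 has an =100% row with a confidence interval for Month 1. Its programming note says: "Repeat for months 2, 3, 6, 9, 12, 15, 18, 21, 24, 27, 30, 33, and 36". Neither the shell nor its footnotes mention that the window behind the label changes.

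**The concern.** Dividing by days makes a seizure frequency comparable between a 30-day and a 90-day window. It does not do so for a criterion of zero seizures, because a subject has three times as long in which to fail it. A reader of Table 14.2.2.1 sees Month 3 followed by Month 6 under the same heading and will take the two =100% rows as the same quantity at two times.

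At stake is the reading of long-term effect. All subjects start at one dose for the first month and may be adjusted afterwards. A fall in seizure freedom after Month 3 that comes from the window could look like waning effect, or could hide a gain after dose adjustment. The table is marked for the interim analysis and the 120-day update, and its replicate for the Japan report.

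**Working it through.** **1. Window lengths** (last day - first day + 1, from Table 7a)

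- Months 1, 2, 3: Days 1-30, 31-60, 61-90, so 30 days each.
- Month 4-6: 180 - 91 + 1 = 90 days. The other later entries are also 90 days, with two exceptions.
- Month 22-24: 730 - 631 + 1 = 100 days.
- Month 34-36: 1095 - 1001 + 1 = 95 days.

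**2. Direction.** A subject with no seizure in 90 days has none in any 30 of those days, but not the reverse. If the seizure process does not change, the =100% proportion in the longer window is equal or lower. This needs no model.

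**3. Size.** The SAP gives no on-treatment seizure rates and no figure to reproduce, so everything below rests on stated assumptions.

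*(a) One common rate m per 28 days, independent seizures.* P(none in d days) = exp(-m x d/28).

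| m per 28 days | 30 days | 90 days | Ratio |
|---|---|---|---|
| 0.1 | 89.8% | 72.5% | 1.2 |
| 0.25 | 76.5% | 44.8% | 1.7 |
| 0.5 | 58.5% | 20.0% | 2.9 |
| 1 | 34.3% | 4.0% | 8.5 |

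For example, at m = 1: exp(-30/28) = 0.343 and exp(-90/28) = 0.040. The 95- and 100-day windows add a smaller distortion. At m = 0.5 they give 18.3% and 16.8%, against 20.0% for 90 days.

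*(b) Rates differ between subjects: gamma, mean 1 per 28 days, shape k (small k means strong heterogeneity).* P(none in d days) = (1 + d/(28k))^(-k).

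| k | 30 days | 90 days | Ratio |
|---|---|---|---|
| 2 | 42.4% | 14.7% | 2.9 |
| 1 | 48.3% | 23.7% | 2.0 |
| 0.5 | 56.4% | 36.7% | 1.5 |
| 0.25 | 66.0% | 51.8% | 1.3 |

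*(c) Clustering.* If all seizures came in clusters of three, 1 seizure per 28 days would be 1/3 cluster per 28 days. Then exp(-30/84) = 70.0% and exp(-90/84) = 34.3%, a ratio of 2.0.

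*(d) Simulated mixed population.* Baseline is lognormal with median 14 per 28 days and is counted over 42 days. The treatment ratio is lognormal and counts are Poisson.

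- Median reduction 55% (log SD of the ratio 1.0): =100% is 5.9% on 30 days and 1.1% on 90 days.
- Median reduction 75% (log SD 1.2): =100% is 13.6% and 4.1%.

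**4. The other thresholds.** In the first simulated scenario the >=50% rate is 54.5% versus 54.3%, and the >=75% rate is 31.2% versus 29.4%. Over a wider set of lognormal scenarios, some with extra within-subject variation, the 30-day to 90-day ratio was 1.00-1.15 for >=50% and 1.01-1.46 for >=75%. For a single subject with 20 seizures per 28 days at baseline, the >=75% shift can go either way. With a true 60% reduction the chance of meeting it is 14.4% on 30 days and 2.8% on 90. With a true 80% reduction it is 73.9% and 84.6%.

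**The case against.** The change of interval is not concealed. Section 6.3.1 says that the period after Month 3 is shown in three-month intervals. Table 7a gives range labels for output, and the main seizure-frequency shell (Table 14.2.1.1.1) uses them. The note in Table 14.2.2.1 can be read as shorthand for the same windows. This stands as far as it goes, but a range label tells the reader which days are covered. It does not say that a zero-seizure proportion is not comparable across ranges.

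The endpoint is secondary and descriptive. No test of Month 3 against Month 6 is planned. Section 6.3.2.3 also reports the whole OLE period and Month 2 to EOS. The longest seizure-free interval and seizure-free days per 28 days do not use the step from 30 to 90 days in this way. All this stands and limits the consequence.

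A reader might infer three stronger claims:

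- **That the seizure-free rate will fall several-fold.** The document gives neither on-treatment rates nor their spread between subjects. Part 3 of the check gives ratios from 1.2 to 8.5.
- **That the final table will show a sharp loss.** Doses may be adjusted after Month 1 and subjects drop out, so true rates and denominators may also change. What can be said is that window length confounds the comparison.
- **That the high-response thresholds in general are distorted.** The >=75% shift is small and has no fixed direction for an individual, and >=50% barely moves.

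**Conclusion.** The point holds for the =100% row. Following the plan exactly gives a month-labelled series in which the seizure-free proportion is measured over 30 days up to Month 3 and over 90-100 days afterwards. Under an unchanged seizure process this can only push the later figures down or leave them equal. That direction is certain from Table 7a and the definition.

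The size is not known. With one common rate it runs from 89.8% versus 72.5% at 0.1 seizure per 28 days, through 58.5% versus 20.0% at 0.5, to 34.3% versus 4.0% at 1. With strong between-subject heterogeneity or clustering it can be only about 1.3- to 2-fold. This is an error of comparability in a secondary, descriptive table. It leaves the >=50% responder rate essentially untouched and affects >=75% only slightly.

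**What to change.** In section 6.3.2.3 and Table 14.2.2.1, and in its Japan replicate, keep the planned rows and add an equal-length comparison for =100% from the existing diary data. Either of two forms would do:

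- a pooled Days 1-90 (Month 1-3) row to set against the later 90-day windows, with the Month 22-24 and Month 34-36 windows cut to 90 days for this row; or
- a supplementary row for the last 30 days of each later interval, for example Days 151-180 for Month 4-6, to set against Months 1-3.

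With equal windows, an unchanged seizure process gives equal expected proportions among the same subjects, so the built-in step disappears. The first form discards almost no data. The second should be added and should not replace the 90-day result, because it leaves out two-thirds of each 90-day window.

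In either case, use the Table 7a labels with day ranges in place of single-month labels, and footnote that =100% rates are not comparable across windows of different length.

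The cost is one extra derivation and some extra rows, plus noisier proportions if the 30-day form is chosen. No new data are needed.

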6.3.2.4 Duration of the Longest Interval between Seizures

The duration of the longest interval (in days) between convulsive seizures will be analyzed.

For each subject, the longest interval between convulsive seizures will be calculated over the entire OLE period. This will be derived as the maximum of the number of days between consecutive convulsive seizures. The intervals between consecutive convulsive seizures (gaps) will be calculated as below, after which the longest interval between convulsive seizures will be derived.

If a subject has two consecutive days of missing diary data, the current seizure-free interval will be ended on the first date of missing diary data, and a new one begun on the next date that diary data are available and no seizure occurs. [In that case, for purpose of calculation of this variable, all intervening days, after the 2nd day, with missing diary data, will be assumed to have a convulsive seizure occurrence, until the first available date with non-missing diary data.]

Let Date0 (=Day1) be the first day of treatment. If convulsive seizures occur on five days having dates as Date1, Date2, Date3, Date4 and Date5, where Date5 > Date4 > Date3 > Date2 > Date1 \geq Date0, and let LDT = Last date of treatment in the OLE treatment period, where LDT \geq Date5, then the time interval between convulsive seizures will be calculated as follows:

$$I1 = \text{Date2} - \text{Date1}$$

$$I2 = \text{Date3} - \text{Date2}$$

$$I3 = \text{Date4} - \text{Date3}$$

$$I4 = \text{Date5} - \text{Date4}$$

For completeness, we calculate the time to the first seizure as

$$I0 = \text{Date1} - \text{Date0}$$

and the time from the last seizure to end of treatment as

$$I5 = \text{LDT} - \text{Date5}$$

Here the duration of the longest interval = Maximum (I0, I1, I2, I3, I4, I5).

If the subject does not experience a seizure during treatment, then the last available diary date will be used to compute the duration of the longest interval as follows:

$$\text{The longest interval} = \text{last available diary date} - \text{Date0}$$

The median time of the longest convulsive seizure-free interval will be presented. Additional summary statistics will be presented, including mean, minimum, maximum, and the 25th and 75th percentiles, 95% confidence intervals for the percentiles using the normal approximation to the binomial distribution. Analyses will be presented for the mITT population (excluding de novo subjects), de novo mITT subjects, and all mITT subjects.

A boxplot of the duration of the longest interval (in days) between seizures will be presented. The boxplot will be presented for the mITT population (excluding de novo subjects), de novo mITT subjects, and all mITT subjects.

A summary of the recurrences of seizures and the gap times between seizures will also be presented. [The duration of the longest interval between convulsive seizures is closely related to the maximum gap time.]

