Current Dose	Taper Step 1 Days 1-4 after study completion or early termination	Taper Step 2 Days 5-8 after study completion or early termination	Taper Step 3 Days 9-14 after study completion or early termination
ZX008 0.2 mg/kg/day	Not applicable	Not applicable	Not applicable
ZX008 0.4 mg/kg/day	ZX008 0.2 mg/kg/day	Not applicable	Not applicable
ZX008 0.5 mg/kg/day	ZX008 0.4 mg/kg/day	ZX008 0.2 mg/kg/day	Not applicable

Note: maximum daily dose of ZX008 is 20 mg.

Regimen 3 = CLB + VPA + STP + ZX008 0.2 mg/kg

Seizure data from the Taper period will not be included in the planned effectiveness endpoints except where specified. However, all safety data obtained including data obtained through the taper period, will be included in the safety analyses.

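### SAP 6.3.2.4 is inconsistent for subjects with no recorded convulsive seizure: their longest-interval formula has no place for diary gaps and a different end date from everyone else's

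*SAP*

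**What the plan says.** The duration of the longest interval between convulsive seizures is a secondary objective (SAP 2.2). Section 6.3.2.4 defines it in three steps.

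- **Scope and gap rule.** For each subject "the longest interval between convulsive seizures will be calculated over the entire OLE period". After two missing diary days in a row, "the current seizure-free interval will be ended on the first date of missing diary data". A fresh interval opens once entries resume without a seizure. Intervening days after the second "with missing diary data, will be assumed to have a convulsive seizure occurrence, until the first available date with non-missing diary data".
- **Subjects with seizures.** The value is the maximum of I0 (Day 1 to first seizure), the differences between successive seizure dates, and the time from the last seizure to LDT, defined as "Last date of treatment in the OLE treatment period".
- **Subjects without seizures.** "If the subject does not experience a seizure during treatment, then the last available diary date will be used to compute the duration". The formula is one subtraction, last available diary date minus Date0, where Date0 is Day 1.

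On the taper, the last paragraph of 3.3.2.2 states: "Seizure data from the Taper period will not be included in the planned effectiveness endpoints except where specified". Section 6.3.2.4 does not mention the taper.

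**The concern.** The no-seizure formula is a single span, so a diary gap has nowhere to enter. The formula for subjects with seizures has no explicit gap term either, but it is a maximum over segments and can take extra ones. The SAP does not say whether the gap rule or the no-seizure formula prevails, nor whether an assumed seizure inside a longer gap moves a subject out of the no-seizure branch. A gap of exactly two days creates no assumed seizure, so the no-seizure branch plainly applies there. The shell for Table 14.2.3.1 has no programming note on gaps. Two competent programmers could therefore report different values for the same subject.

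The end dates differ as well. LDT lies within the OLE treatment period. The last available diary date is not bounded at Visit 16, and Table 4 shows diaries still being collected at Visit 17. The key seizure-frequency endpoints in Table 7a do carry a bound, the earlier of last dose and Visit 16.

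The subjects affected are those most likely to set the maximum and the tail of the boxplot. Some groups are small: the treatment-group table in the TFL shells expects about 40 subjects in ZX 0.5 and 35 de novo. A few values could therefore move a group mean.

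**Working it through.** The SAP gives no expected value for this endpoint, so there is no figure to reproduce. The check applies both rules to one subject with no recorded seizure.

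**Inputs.** Date0 = Day 1, Visit 16 = Day 1085 and Visit 17 = Day 1099 (Table 4). LDT is assumed to be Day 1085. Gap positions are assumed.

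**Formulas.**
- As written: last diary day − 1.
- Gap rule: each segment runs from its first available day to the first missing day of the next gap of two or more days, or to Day 1085. The longest segment is taken.

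| Diary pattern | As written, diary to Visit 16 | As written, diary to Visit 17 | Gap rule, end Day 1085 |
|---|---|---|---|
| No gap | 1085 − 1 = 1084 | 1099 − 1 = 1098 | 1084 |
| Days 31–32 missing | 1084 | 1098 | max(31 − 1, 1085 − 33) = 1052 |
| Days 540–541 missing | 1084 | 1098 | max(540 − 1, 1085 − 542) = 543 |
| Days 360–361 and 720–721 missing | 1084 | 1098 | max(359, 358, 1085 − 722) = 363 |
| Diary stops for good after Day 900 | 900 − 1 = 899 | 899 | 901 − 1 = 900 |

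One mid-study 2-day gap gives 1084/543, a ratio of about 2.0. An early 2-day gap gives 1084/1052, about 1.03. A diary that stops for good gives no inflation. Counting diary days up to Visit 17 adds at most 1099 − 1085 = 14 days, and 14/1084 = 1.3%.

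**Range over gap frequency (assumed).** Random 2-day gaps were simulated over 1085 days, 2000 diaries per setting, all without a seizure:

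| Average gaps per subject | Mean under gap rule (days) | 1084 ÷ mean |
|---|---|---|
| 0.5 | 953 | 1.14 |
| 1.1 | 846 | 1.28 |
| 2.2 | 691 | 1.57 |
| 5.4 | 448 | 2.42 |

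These ratios describe simulated seizure-free diaries, not trial subjects.

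**The case against.** The gap rule is worded for any subject, precedes both formulas and exempts no one. A programmer may reasonably apply it to seizure-free subjects too. A reader might infer that the SAP deliberately lets these subjects run across every gap while all others are cut. The text does not say that; it leaves two rules unreconciled. For a gap of three days or more, the section's own assumed seizures would, on a natural reading, move the subject into the branch that takes a maximum over intervals. Only a gap of exactly two days escapes that imputation, and the gap rule still covers it. This stands, and it makes the point an inconsistency rather than a fixed bias.

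A reader might also infer that taper days are counted. Section 3.3.2.2 excludes them unless specified, and 6.3.2.4 specifies nothing. On the other side, 6.1.5.1 places the taper inside the OLE Phase, and the interval is said to cover the whole OLE period. The question is open, but it is worth at most about 14 days.

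Using the last diary date can be the cautious choice, since it credits no unobserved tail when the diary stops early. That stands as well.

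The one-day counting convention (consecutive seizure days score 1, while D seizure-free days score D − 1) is not part of the problem. It is a consistent date difference, and it works slightly against seizure-free subjects.

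Finally, the endpoint is only described, with no test, and the formula reaches only subjects with no convulsive seizure throughout treatment. De novo entry required at least four per 4 weeks, so such subjects may be few. The median and quartiles move only if enough subjects qualify.

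**Conclusion.** The point holds as an internal inconsistency with a conditional effect. Programmed as written, the no-seizure formula overstates the interval for a seizure-free subject with a diary gap of two or more days: anywhere from slightly (1084 against 1052) to about double (1084 against 543) for a single 2-day gap, and more with several gaps. This assumes Visit 16 on Day 1085, LDT on the same day and the stated gap positions.

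The documents do not support saying that reported values are inflated in general, or that the median or upper quartile will shift. The SAP gives neither the proportion of seizure-free subjects nor a diary-missingness rate. What can be said is that any error of this kind credits unobserved days as seizure freedom, and that it falls on the subjects who set the maximum and upper tail of a secondary-objective endpoint. It should be corrected.

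**What to change.** Replace the no-seizure formula in 6.3.2.4 with the longest gap-free segment, so that the two-consecutive-missing-day rule applies to every subject whether or not a seizure was recorded. End the final interval for all subjects at the earliest of LDT, Visit 16/ET and the last non-missing diary date within the OLE Treatment Period. Leave the day count as it is. Add the same rule as a programming note to the shells for Table 14.2.3.1, Figure 14.2.3.2 and Listing 16.2.6.3.

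The cost is a few lines of SAP wording and code, with no new data collection. The downside is that some reported maxima become shorter.
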